#### 6.2. Clinical Laboratory Tests

Descriptive statistics will be presented for all chemistry (including the lipid panel), hematology (including hemoglobin A1c [HbA1c]), and urinalysis (pH and specific gravity) laboratory parameters at each scheduled time point. In addition, change from baseline to all postbaseline time points will be summarized for chemistry, hematology, and urinalysis (pH and specific gravity) parameters and displayed by treatment group.

The number and percentage of subjects with treatment-emergent postbaseline markedly abnormal postbaseline values will be presented by treatment group. Clinical laboratory test values will be considered "treatment-emergent markedly abnormal" (TEMA) using the criteria defined by the sponsor listed in Attachment 3. The identification of TEMA laboratory values is based on the postbaseline value being out of range while the baseline value is either missing or within the range given in Attachment 3. If postbaseline laboratory results are above the upper limit and the baseline value is below the lower limit, then the postbaseline abnormality will also be considered TEMA. The same applies to the postbaseline value being below the lower limit with the baseline value being above the upper limit.

In addition, the number of subjects with the following shifts in chemistry laboratory values from baseline to the maximum postbaseline time point will be presented:

- Glucose:
  - from <100 mg/dL to  $\geq 126 \text{ mg/dL}$  (normal to high)
  - from <100 mg/dL to  $\geq 100 \text{ mg/dL} <126 \text{ mg/dL}$  (normal to borderline high)
  - from [ $\geq 100 \text{ mg/dL} \langle 126 \text{ mg/dL} \rangle$ ] to  $\geq 126 \text{ mg/dL}$  (borderline high to high)
- Triglycerides:
  - $\circ$  from <150 mg/dL to  $\geq$ 200 mg/dL (normal to high/very high)
  - o from <150 mg/dL to  $\geq 500 \text{ mg/dL}$  (normal to very high)
  - $\circ~$  from [ $\geq \! 150~mg/dL$   $<\!\! 200~mg/dL$ ] to  $\geq \! 200~mg/dL$  (borderline high to high/very high)
  - o from [ $\geq$ 150 mg/dL <200 mg/dL] to  $\geq$ 500 mg/dL (borderline high to very high)
  - o from [ $\geq 200 \text{ mg/dL} \langle 500 \text{ mg/dL} \rangle$ ] to  $\geq 500 \text{ mg/dL}$  (high to very high)
- Total Cholesterol

- $\circ$  from <200 mg/dL to  $\geq$ 200 mg/dL (normal to borderline high/high)
- $\circ$  from <200 mg/dL to  $\geq$ 240 mg/dL (normal to high)
- $\circ$  from <200 mg/dL to [ $\geq$ 200 mg/dL <240 mg/dL] (normal to borderline high)
- from [ $\geq 200 \text{ mg/dL} \langle 240 \text{ mg/dL} \rangle$ ] to  $\geq 240 \text{ mg/dL}$  (borderline high to high)
- HDL Cholesterol: from  $\geq$ 40 mg/dL to <40 mg/dL (normal to low).

The following conversion rules will be used: Glucose 1 mg/dL=0.05551 mmol/L; Triglycerides 1 mg/dL=0.01129 mmol/L; Total Cholesterol, HDL Cholesterol 1 mg/dL=0.02586 mmol/L.

The incidence of subjects with treatment-emergent ALT values >3\*upper normal limit (ULN) or AST > 3\* ULN will be presented for the double-blind phase. Additionally, incidence of treatment-emergent hepatic toxicity (Hy's Law) defined as (ALT values >3\*ULN or AST > 3\* ULN) AND total bilirubin values >2\*ULN will be presented for the double-blind phase. Similar to the markedly abnormal analysis, only subjects with baseline (ALT values  $\leq$ 3\*ULN or AST  $\leq$ 3\*ULN) (AND baseline total bilirubin values  $\leq$ 2\*ULN for hepatic toxicity) (or if baseline value is missing) will be eligible for these analyses.

A listing of subjects with markedly abnormal laboratory values will be provided.

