9. STUDY EVALUATIONS

9.1. Study Procedures

9.1.1. Overview

The Time and Events Schedule summarizes the frequency and timing of efficacy, PK, biomarker, pharmacogenomic, and safety measurements applicable to this study.

Throughout the study, subjects will complete self-assessments (PRO) at the study site. Where multiple procedures are scheduled for the same visit, procedures are recommended to be performed in the following order: salivary cortisol samples, ECGs, vital signs, blood samples, PRO assessments and then other procedures. All scheduled morning salivary cortisol samples should be collected upon awakening and evening salivary cortisol samples should be collected at bedtime. The salivary cortisol samples scheduled at the time of PK samples (ie, Day 1 night, Day 2 morning, and Day 8 morning) should be collected before any blood samples are drawn.

Blood collections for PK, biomarker, and pharmacogenomic and epigenetic (DNA) assessments should be kept as close to the specified time as possible. Actual dates and times of assessments will be recorded in the source documentation.

Serum or urine pregnancy tests may be performed, as determined necessary by the investigator to establish the absence of pregnancy at any time during the subject's participation in the study. For WOCBP, who enrolled in the study before Amendment 5 and who continue in the trial, a serum pregnancy test must be performed at screening, and urine pregnancy tests must be performed at Day 1, Day 22, Day 42 (End-of Treatment/Early Withdrawal), and at the Follow-up Visit to establish absence of pregnancy.

The total blood volume to be collected from each subject will be approximately 190 mL. Repeat or unscheduled samples may be taken for safety reasons or for technical issues with the samples. The maximum amount of blood drawn (including retesting) from each subject in this study will not exceed 300 mL.

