#### 2.5. Visit Windows

As subjects do not always adhere to the protocol visit schedule, the following rules are applied to assign actual visits to analysis visits. Listed below are the visit windows and the target days for each visit. The reference day is Study Day 1 (which is the first day the study drug was taken in the double-blind phase). If a subject has 2 or more actual visits in one visit window, the visit closest to the target day will be used as the protocol visit for that visit window. The other additional visit(s) will not be used in the summaries or analyses but they can be used for determination of clinically important end points. If 2 actual visits are equidistant from the target day within a visit window, the later visit is used.

All assignments will be made in chronological order. Once a visit date is assigned to a visit window, it will no longer be used for a later time point except for the end point (DB). Listed below (Table 1) are the visit windows and the target days for each visit defined in the protocol.

Assessments prior to Day 1 of the double-blind phase that are not considered a baseline assessment will be labeled as 'Screening'.

Parameter	Analysis Phase	Scheduled Visit Number	Time Interval (label on output)	Time Interval (Day)*	Target Time Point (Day/Time)
MADRS	Screening	1	Screening	< 1	-28 to -3
	DB	2	Baseline	≤1	1
		3	Day 8	2 to 15	8
		4	Day 22	16 to 32	22

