#### Attachment 2: Conversion of Raw Score to T-Score for PROMIS-Fatigue

Fatigue 8a				
Short Form Conversion Table				
Raw Score	T-score	SE*		
8	33.1	4.8		
9	38.5	2.7		
10	41.0	2.2		
11	42.8	2.0		
12	44.3	1.9		
13	45.6	1.8		
14	46.9	1.8		
15	48.1	1.8		
16	49.2	1.8		
17	50.4	1.8		
18	51.5	1.7		
19	52.5	1.7		
20	53.6	1.7		
21	54.6	1.7		
22	55.6	1.7		
23	56.6	1.7		
24	57.5	1.7		
25	58.5	1.7		
26	59.4	1.7		
27	60.4	1.7		
28	61.3	1.7		
29	62.3	1.7		
30	63.3	1.7		
31	64.3	1.7		
32	65.3	1.7		
33	66.4	1.7		
34	67.5	1.7		
35	68.6	1.7		
36	69.8	1.8		
37	71.0	1.8		
38	72.4	2.0		
39	74.2	2.4		
40	77.8	3.7		

\*SE = Standard Error

	Markedly Abnormal Limits	
Laboratory Parameter (unit)	Low	High
Clinical Chemistry		
Albumin $(g/dL)$ but SI unit = $g/L$	2.4→24	6.0 →60
Alkaline phosphatase (U/L)	N/A	250
Alanine transaminase (SGPT) (U/L)	N/A	200
Aspartate transaminase (SGOT) (U/L)	N/A	250
Bicarbonate (mEq/L) but SI unit=mmol/L	15.1→15.1	34.9→34.9
Bilirubin (direct) (mg/dL) but SI unit = $\mu$ mol/L	N/A	$3.0 \text{ mg/dL} \rightarrow 51.3 \text{ umol/L}$
Bilirubin (total) (mg/dL) but SI unit = $\mu$ mol/L	N/A	$3.0 \text{ mg/dL} \rightarrow 51.3 \text{ umol/L}$
Blood urea nitrogen (mg/dL) but SI unit=mmol/L	N/A	$50 \text{ mg/dL} \rightarrow 17.9 \text{ mmol/L}$
Calcium (mg/dL) but SI unit= $mmol/L$	$6 \rightarrow 1.497 \text{ mmol/L}$	$12 \rightarrow 2.994 \text{ mmol/L}$
Chloride (mEq/L or mmol/L)	94	112
Cholesterol ( $mg/dL$ ) but SI unit=mmol/L	N/A	$300 \rightarrow 7.758 \text{ mmol/L}$
Creating kinase (U/L)	N/A	990
Creatining $(mg/dL)$ SL unit=umol/L	N/A	$3 \rightarrow 265.2  \mu\text{mol/I}$
Gamma glutamyl transferase (U/L)	N/A	300 U/I
Glucose Plasma (mg/dL) but SL unit=mmol/L	$40 \rightarrow 2.204 \text{ mmol/I}$	$300 \rightarrow 16.653 \text{ mmol/I}$
High-density linoprotein cholesterol (HDL) (mg/dL)	$35 \rightarrow 0.905$	500 7 10:055 mm0/L N/Δ
but SI unit=mmol/L	55 70.905	1V/ $A$
Lactic acid dehydrogenase (LDH) (U/L)	N/A	500
Low-density lipoprotein cholesterol (LDL) (mg/dL)	89→ 2.3015	160 → 4.1376 mmol/L
but SI unit=mmol/L		
Phosphate (mg/dL) but SI unit=mmol/L	2.2 → 0.71038 mmol/L	8.1→ 2.61549 mmol/L
Potassium (mmol/L)	3.0	5.8
Sodium (mEq/L) but SI unit = $mmol/L$	125→125	155→155
Total protein (g/L)	50	N/A
Triglycerides (mg/dL) but SI unit=mmol/L	N/A	500 → 5.645 mmol/L
Uric acid (mg/dL) but SI unit=µmol/L	1.5→89.22	10 → 594.8 µmol/L
Hematology		•
Hematocrit (%) – female	0.28	0.50
- male	0.24	0.55

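### The chemistry shift table uses the maximum postbaseline value for HDL as well, where the minimum is the adverse extreme; only subjects with discordant repeat HDL values are affected

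*SAP*

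**What the plan says.** SAP 6.2 (Clinical Laboratory Tests) introduces the shift table with one sentence for all listed analytes: "shifts in chemistry laboratory values from baseline to the maximum postbaseline time point will be presented". The categories under glucose, triglycerides and total cholesterol all go up, for example "borderline high to high/very high". The last entry is HDL cholesterol, and it goes down: from at least "40 mg/dL to <40 mg/dL (normal to low"). No separate minimum rule is given for HDL.

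The Time and Events Schedule has the lipid panel at Day 1 and at Day 42/early withdrawal only. SAP 2.5, Table 1, gives it a single postbaseline visit window, from Day 2 to the end of the double-blind phase, plus the double-blind end point.

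Protocol 9.1.1 allows further samples: "Repeat or unscheduled samples may be taken for safety reasons or for technical issues with the samples". On extra visits within one window, SAP 2.5 says: "The other additional visit(s) will not be used in the summaries or analyses but they can be used for determination of clinically important end points".

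**The concern.** A shift table of this kind is meant to show each subject's worst excursion. For an upward shift the maximum does that. For a shift to low it does the reverse, because one value at or above 40 mg/dL cancels any number of values below it. A programmer following the sentence literally would take the maximum for HDL.

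At stake is the count of subjects moving to low HDL, which is the only HDL direction the table reports. Safety and tolerability is one of the two primary objectives, and Protocol 1.3 names metabolic syndrome as a tolerability concern with existing adjunctive drugs. A metabolic table should therefore not lean towards showing no shift.

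**Working it through.** The plan gives no figure to reproduce here. The check is one of logic, followed by an illustration on assumed inputs.

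**Direction.** Take a subject with baseline HDL of at least 40 and postbaseline values v1, ..., vk.

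- Rule as written: shift if max(v1, ..., vk) < 40, which requires every value to be below 40.
- Worst-value rule: shift if min(v1, ..., vk) < 40, which requires at least one value below 40.

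The first condition implies the second, so the written rule gives the same count or a lower one, never a higher one.

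**When the rules differ.**

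| Postbaseline HDL values | Maximum rule | Minimum rule |
|---|---|---|
| One value (the scheduled case) | v < 40 | v < 40, identical |
| Two values, both at or above 40 | no shift | no shift |
| Two values, both below 40 | shift | shift |
| Two values, one on each side of 40 | no shift | shift |

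Only the last row is affected. It needs a second HDL value, and the schedule does not produce one.

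**Backstop.** SAP Attachment 3 sets the markedly low HDL limit at 35 mg/dL, given as 0.905 mmol/L. With the SAP's conversion factor, 35 × 0.02586 = 0.905, so the limit is internally consistent. The shift threshold is 40 × 0.02586 = 1.034 mmol/L. The markedly abnormal count is "based on the postbaseline value being out of range while the baseline value is either missing or within the range" and is not tied to a maximum. It would catch a value below 35, but not one from 35 to below 40.

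**Illustrative size.** None of these inputs comes from the documents. Assume a between-subject mean of 52 and SD of 13 mg/dL, a within-subject SD of 3 to 7, a mean change of 0 or −3, and a fraction f of subjects with a second value taken at random. Let p_max and p_min be the simulated shift rates, among subjects with baseline of at least 40, when two values exist. The gap between the rules is f × (p_min − p_max).

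| Within-subject SD, mean change | p_max | p_min | Gap, f = 0 | Gap, f = 5% | Gap, f = 20% |
|---|---|---|---|---|---|
| 3, 0 | 1.88% | 6.42% | 0 | 0.05 × 4.54 = 0.23 points | 0.20 × 4.54 = 0.91 points |
| 5, 0 | 2.92% | 10.94% | 0 | 0.05 × 8.02 = 0.40 points | 0.20 × 8.02 = 1.60 points |
| 7, −3 | 7.03% | 22.85% | 0 | 0.05 × 15.82 = 0.79 points | 0.20 × 15.82 = 3.16 points |

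The first and last rows are the smallest and largest gaps over the combinations tried. The f = 0 column is the planned schedule.

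**The case against.** The strongest reply is that nothing planned is affected. One scheduled postbaseline lipid sample makes the maximum and the minimum the same number. That stands.

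Second, repeat values may never reach this table. SAP 2.5 keeps the visit closest to the target day and drops the others from summaries, apart from clinically important end points. Section 6.2 does not say whether this table is such an end point. Where the SAP wants unscheduled values in a maximum, it says so, as in SAP 6.4 for ECG. The word maximum also has a use without repeat HDL values, because glucose is in the serum chemistry panel, which is scheduled at both Day 8 and Day 42. This stands as an ambiguity. It does not show that repeats are excluded.

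Third, HDL is reported elsewhere: "change from baseline to all postbaseline time points will be summarized for chemistry, hematology, and urinalysis", and there is a markedly abnormal count and listing. These help, but mean changes do not count subjects crossing 40, and the markedly abnormal limit is 35.

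Fourth, the SAP speaks of a maximum time point, not a maximum value. The phrase is loose. The highest value is the natural reading beside a list of upward shifts, and the looseness is itself a reason to edit the sentence.

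A reader might infer that the metabolic summary will understate HDL falls in general, or that every subject with a repeat HDL value is misclassified towards no shift. The documents support neither. The first fails on the single scheduled sample. The second fails because concordant values classify the same way under both rules.

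**Conclusion.** The rule points the wrong way for HDL as written. Any resulting error is an undercount of shifts to low. On the scheduled data the effect is zero. It is above zero only when three things hold together: a repeat or unscheduled double-blind HDL value exists, it enters the table, and the subject's values lie on both sides of 40 mg/dL. If the low value is from 35 to below 40, the markedly abnormal count misses it as well.

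The gaps of 0.23 to 0.79 percentage points (5% of subjects with a second value) and 0.91 to 3.16 points (20%) rest wholly on assumed HDL distributions and repeat rates. They show scale and are not estimates for this trial. This is a minor wording correction with no bearing on the primary analysis.

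**What to change.** Reword the sentence that introduces the shift table in SAP 6.2 so that shifts run from baseline to the maximum postbaseline value (minimum for HDL cholesterol) during the double-blind phase. Add one sentence saying whether unscheduled and repeat values are included, as SAP 6.4 does for ECG, so that the link to the visit-window rule in SAP 2.5 is settled before programming.

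The cost is a few words in the SAP and a minimum in place of a maximum for one analyte in the table program. No new data or extra samples are needed, and no other analysis changes.

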 - 4.4 Is receiving monotherapy treatment for depressive symptoms with one of the following SSRI/SNRI antidepressants, in any formulation: citalopram, duloxetine, escitalopram, fluvoxamine, fluoxetine, milnacipran, levomilnacipran, paroxetine, sertraline, venlafaxine, desvenlafaxine, vilazodone, or vortioxetine at a stable dose (at or above the minimum therapeutic dose level) for at least 4 weeks, and for no

greater than 12 months, at screening. Modification of an effective preexisting therapy should not be made for the explicit purpose of entering a subject into the study.

Note: Dose and duration of treatment should be verified by the investigator using the medical or pharmacy records. The investigator will use this information to complete the MGH-ATRQ, which will then be corroborated by the independent rater.

- 5. 5.1 Criterion Modified per Amendments 1 and 3
 - 5.2 Have a MADRS total score ≥25 (performed by independent, centralized remote raters) at screening and must not demonstrate a clinically significant improvement (ie, an improvement of >20% on their MADRS total score) from the screening to baseline visit.
- 6. Criterion Modified per Amendment 3
 - 6.1 Body mass index (BMI) between 18 and 35 kg/m² inclusive (BMI=weight/height²).
- 7. Must be an outpatient at screening.
- 8. Criterion Modified per Amendment 3
 - 8.1 Must be otherwise healthy on the basis of physical examination, medical history, vital signs, 12-lead ECG, and clinical laboratory tests performed at screening. If the results of the clinical laboratory tests are outside the normal reference ranges, the subject may be included only if the investigator judges the abnormalities or deviations from normal to be not clinically significant or to be appropriate and reasonable for the population under study. This determination must be recorded in the subject's source documents and initialed by the investigator.
- 9. 9.1 Criterion Modified per Amendments 2 and 3
 - 9.2 Must sign an informed consent form (ICF) indicating that he or she understands the purpose of and procedures required for the study and be willing to participate in the study.
- 10. Criterion Deleted per Amendment 5
- 11. Criterion Deleted per Amendment 5
- 12. Criterion Modified per Amendment 5
 - 12.1 A woman must agree not to donate eggs (ova, oocytes) for the purposes of assisted reproduction during the study and for a period of at least 1 month after receiving the last dose of study drug.

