4.2. Exclusion Criteria

Any potential subject who meets any of the following criteria will be excluded from participating in the study:

- 1. 1.1 Criterion Modified per Amendments 3 and 5
 - 1.2 Has a history of, or current signs and symptoms of, severe renal insufficiency (creatinine clearance <30 mL/min); moderate to severe hepatic insufficiency (Child-Pugh Score 7-9), significant or unstable cardiovascular, respiratory, gastrointestinal, neurologic (including narcolepsy), hematologic, rheumatologic, immunologic or endocrine disorders (including uncontrolled hypo- or hyperthyroidism or diabetes, or insulin-dependent diabetes mellitus). Subjects with non-insulin dependent diabetes mellitus who are well-controlled (hemoglobin $A1_C$ [HbA1_C] \leq 7.5% and fasting glucose <126 mg/dL at screening) may be eligible to participate if otherwise medically healthy, and if on a stable regimen of glucose-lowering medications for at least 2 months prior to screening.
- 2. Criterion Modified per Amendment 1
 - 2.1 Has current signs/symptoms of hypothyroidism or hyperthyroidism (Subjects with known hypothyroidism who have been on stable treatment for at least 3 months prior to screening are required to have thyroid-stimulating hormone [TSH] and free thyroxine [FT₄] obtained. Any subject with an elevated TSH should also have FT₄ measured. In any case where the TSH value is out of range, but FT₄ is normal, the findings should be discussed directly with the medical monitor before the subject is enrolled. If the FT₄ value is out of range, the subject is not eligible. Subjects taking thyroid supplementation for antidepressant purposes are not allowed in the study).

3. Has signs and symptoms of Cushing's Disease, Addison's Disease, primary amenorrhea, or other evidence of significant medical disorders of the HPA axis.

4. Criterion Modified per Amendment 1

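### The baseline condition for treatment-emergent ALT/AST above 3×ULN joins the two enzymes with 'or', so an unchanged single-enzyme elevation counts as treatment-emergent

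*SAP*

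**What the plan says.** SAP 6.2 (Clinical Laboratory Tests) plans two liver summaries. The first is stated as "The incidence of subjects with treatment-emergent ALT values >3\*upper normal limit (ULN) or AST > 3\* ULN will be presented for the double-blind phase". The second, for Hy's law, takes the same enzyme event and adds bilirubin: "AND total bilirubin values >2\*ULN will be presented for the double-blind phase".

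One sentence sets the baseline condition for both. It begins "Similar to the markedly abnormal analysis, only subjects with baseline (ALT values", continues with the 3×ULN limit, and joins AST to ALT with 'or' before closing the bracket. It then adds bilirubin for Hy's law ("3\*ULN) (AND baseline total bilirubin values" at or below 2×ULN) and ends with the missing-data clause "or if baseline value is missing) will be eligible for these analyses".

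The markedly abnormal (TEMA) rule to which the sentence compares itself stands earlier in SAP 6.2. There, identification is "based on the postbaseline value being out of range while the baseline value is either missing or within the range given in Attachment 3".

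On entry, Protocol 4.1 criterion 8.1 deals with out-of-range screening laboratory results by judgement: "the subject may be included only if the investigator judges the abnormalities or deviations from normal to be not clinically significant", or appropriate and reasonable for the population. Protocol 4.2 criterion 1.2 excludes "moderate to severe hepatic insufficiency (Child-Pugh Score 7-9"). Neither section gives a numeric ALT or AST limit.

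**The concern.** A baseline condition for a treatment-emergent event should remove subjects who already meet the event definition before dosing. The event here is ALT high or AST high. Its negation is ALT not high *and* AST not high. The SAP carries the 'or' into the baseline bracket, where it no longer negates the event, so a subject with one enzyme already above 3×ULN stays in the count.

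Safety and tolerability is a primary objective (SAP 1.1), and liver tables are read case by case. One pre-existing elevation labelled as emergent can suggest a drug effect in an arm where nothing changed.

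**Working it through.** The documents state no figure for this point, so the check is one of logic. Call an enzyme high if it is above 3×ULN and bilirubin high if it is above 2×ULN.

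**Single case.** Baseline ALT 4×ULN and AST 1×ULN, with the same values postbaseline.
- Eligible as written? AST 1×ULN is at or below 3×ULN, so yes.
- Event? ALT 4×ULN is above 3×ULN, so yes.
- Result: counted as treatment-emergent with no change. The mirror case (AST high, ALT not) behaves the same way.

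**All cases, ALT/AST summary.** There are 4 baseline patterns × 4 postbaseline patterns = 16. The table gives the number of patterns counted under three baseline rules. The four patterns with neither enzyme high postbaseline are never counted and are left out.

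| Baseline high | Postbaseline high | As written ('or') | 'And' | Same enzyme |
|---|---|---|---|---|
| Neither | ALT, AST or both (3 patterns) | 3 | 3 | 3 |
| ALT only | ALT only (1) | 1 | 0 | 0 |
| ALT only | AST, with or without ALT (2) | 2 | 0 | 2 |
| AST only | AST only (1) | 1 | 0 | 0 |
| AST only | ALT, with or without AST (2) | 2 | 0 | 2 |
| Both | any (3) | 0 | 0 | 0 |
| **Total** | | **9** | **3** | **7** |

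The text as written counts 9 − 7 = 2 patterns in which no enzyme is newly high. The 'and' rule removes both but also loses 7 − 3 = 4 patterns with a genuinely new rise in the second enzyme. The same-enzyme rule removes the two and keeps the four.

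**Hy's law.** Adding bilirubin at baseline and postbaseline gives 16 × 4 = 64 patterns. With known baselines, only one of the four bilirubin combinations can count under any rule: not high at baseline, high afterwards. The totals are therefore again 9, 3 and 7, with 2 patterns counted as written although no enzyme elevation is new. In those two the bilirubin rise is new.

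**Can such a subject be in the data?** The protocol sets no ALT or AST entry limit. Eligibility laboratory tests are taken at screening, up to 28 days before dosing, whereas SAP 2.4 takes as baseline the closest value before first dose, normally the Day 1 chemistry sample. An elevation accepted at screening, or arising before Day 1, can therefore be the baseline value.

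**Illustrative size.** If the 2:1:1 allocation held throughout, an active arm would have 280 × 1/4 = 70 subjects, and one miscounted subject adds 1/70 = 1.4 percentage points. In an arm of 50 it would be 1/50 = 2.0 points. Both arm sizes are assumptions, because the allocation after the interim analysis is left open.

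**The case against.** The strongest reply is that the sentence says it is similar to the markedly abnormal analysis, which compares each value with its own baseline. On that footing a programmer could read the 'or' enzyme by enzyme, and the stable ALT case would not be counted. This reading is available and is probably what was meant. It does not settle the matter, because both enzymes stand in one bracket as alternative ways to qualify and nothing pairs each enzyme with its own postbaseline value. For the same reason, a reader should not infer that the plan deliberately chose to count pre-existing elevations; its own cross-reference points the other way.

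A reader might also infer that an unchanged baseline picture can become a Hy's law case. With a known bilirubin baseline it cannot, since bilirubin must go from at or below 2×ULN to above it. A new bilirubin rise on top of an elevated enzyme merits case review in any event. What stands is narrower: the enzyme component need not be new.

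A third inference, that the tables will show a false liver signal, goes beyond the documents. They give no baseline frequency of ALT or AST above 3×ULN, subjects must be otherwise healthy, and moderate to severe hepatic insufficiency is excluded. Such entries are likely to be rare, though no numeric limit rules them out.

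Finally, an over-count could be found elsewhere: Protocol 11.7 provides a listing of all results outside reference ranges. That helps a careful reader but leaves the tabulated incidence wrong. The listing in SAP 6.2 covers only markedly abnormal values, with high limits of 200 U/L for ALT and 250 U/L for AST (Attachment 3). It misses some values above 3×ULN wherever the ULN is below 200/3 = 66.7 U/L for ALT or 250/3 = 83.3 U/L for AST.

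**Conclusion.** The definition is wrong as written and should be corrected. Taken literally, SAP 6.2 excludes a subject only if both enzymes exceed 3×ULN at baseline, and so counts a stable single-enzyme elevation as treatment-emergent, against the value-by-value rule that it cites. For Hy's law the defect is confined to the enzyme component when baseline bilirubin is known.

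The error can only over-count. The number of subjects affected cannot be computed from the documents and is probably small; 1.4 percentage points per subject is an illustration that rests on an assumed arm of 70. The summaries are descriptive, and the primary endpoint, significance level and sample size are not touched. The conclusion rests on the literal reading of the bracket; under the enzyme-by-enzyme reading the count would be right, but the text would still need to say so.

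**What to change.** Replace the baseline sentence in SAP 6.2 with a same-enzyme rule:
- **ALT/AST above 3×ULN:** count a subject when ALT or AST exceeds 3×ULN postbaseline in the double-blind phase and that same enzyme's baseline is at or below 3×ULN or missing.
- **Hy's law:** require the above, and also postbaseline total bilirubin above 2×ULN with baseline total bilirubin at or below 2×ULN or missing.

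Do not simply change 'or' to 'and', for the reason shown in the working. Tying the missing-baseline clause to the same analyte also removes the present doubt about which missing value it refers to. If the team wants to keep sight of subjects with a pre-existing enzyme elevation and a new bilirubin rise, list them separately.

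The cost is one rewritten sentence in the SAP and the matching condition in the laboratory program. No data collection changes.
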